3.1 General Design

This is a prospective observational study of patients with normally functioning (competent) and diseased (incompetent) BAVs. Patients will be stratified into two groups based on degree of baseline aortic insufficiency. Those patients with less than moderate (+2) AI will be in the “competent BAV” group, and those patients with greater than moderate (+2) AI will be in the “incompetent BAV” group. Each group will be limited to 30 patients. All patients will follow the same study time course and undergo the same study procedures, including an annual 4D CTA scan. The goal of this work is to describe differences in the anatomical and functional characteristics of BAVs in these two groups based on 4D CTA.

Overview of study procedures (described in Section 5):

- Screening for study eligibility and informed consent
- 4D CTA imaging at baseline and at 1-year intervals over a period of 5 years. (Annual CTA studies will be performed routinely in some or many of the patients, but the 4D protocol will be for research purposes.)
- Annual office visits and echocardiography studies over the 5-year study period (standard of care)

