Medical information and image data collected as standard-of-care at visits other than the scheduled annual follow-up may be included in the patient's research record. For example, relevant information from cardiac imaging studies or office visits other than the annual follow-up will be documented, especially as it relates to the development of AI and/or AS and associated symptoms. If a patient requires aortic valve repair or replacement during the 5-year study period, information that is routinely acquired during the operation will be recorded (e.g., procedures performed, prosthetic devices used, pre- and post-operative imaging and exam measurements, etc.).

5.4 *Subject Withdrawal*

Subjects may withdraw from the study at any time without impact to their care. They may also be discontinued from the study at the discretion of the Investigator for lack of adherence to study procedures or visit schedules. Patients will be followed for any safety events. If a patient meets the indications for valve surgery during their participation in the study, they will remain in the study on their original study timeline, unless they require an aortic valve replacement, at which point they will end their study participation. It will be documented whether or not each subject completes the study.

CONFIDENTIAL

6 Statistical Plan

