6.2.2 Analysis of Primary Outcome of Interest

Post-processing of each 4D CTA data set will involve manual or semi-automatic image segmentation (labeling) and geometrical modeling of the BAV at each cardiac phase. Geometrical and functional measurements (e.g., coaptation area, coaptation height, cusp surface area, aortic root diameters, valve orifice area, localized cusp thickness, and aortic cusp and root velocities) will be extracted from the 4D CTA image segmentations to quantify valve morphology and dynamics at each study time point, as well as longitudinally. Measurements from the competent and incompetent BAV groups will be reported with standard descriptive statistics, including group means and standard deviations time-normalized with respect to the cardiac cycle at each study time point. Comparison of valve measurements in the two groups will be carried out with independent Student t-tests at multiple phases of the cardiac cycle with false discovery rate adjustment to account for multiple comparisons. We will perform additional statistics on longitudinal data. Comparable measurements will be made on standard-of-care echocardiography and/or MR image data when available.

7 Safety and Adverse Events

Potential safety issues in this study are related to radiation and contrast for the 4D CT exam. An internal safety committee, including representation from Radiology and Cardiothoracic Surgery, will monitor for adverse events. All CTs will be reviewed on a quarterly basis concerning radiation dose. Moderate to severe contrast reactions will be reported to the IRB as severe adverse events and evaluated individually by the safety committee. Patients who have severe adverse events will be withdrawn from the study. Mild reactions to contrast will be reviewed quarterly to evaluate whether the participant should continue in the trial.

8 Study Administration, Data Handling and Record Keeping

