10.2 Benefits

There is no direct benefit to study participants. *The 4D CTA acquired in this study will not be used for clinical care or surgical decision-making for the participants but will likely benefit future BAV patients.* The following paragraphs describe the ways in which the study may benefit patients in the future.

This study may benefit BAV patients in the future since it will provide information that can help standardize the approach to BAV repair. For example, the thresholds on cusp height that are used to intraoperatively determine whether a BAV is repairable are based on tricuspid aortic valve data rather than physiologically normal BAVs. This study will produce a much-needed data set on physiologically normal BAV morphology that will provide quantitative evidence for cusp height thresholds and other measurements that drive intraoperative decision making. Thus, the knowledge gained from this study will help to determine whether a future patient is best suited for valve repair or valve replacement based on their pre-operative BAV morphological and dynamic characteristics. By providing descriptive information on how a pathological BAV should look and function after a successful valve repair, this research could make repair a viable and more accessible alternative treatment in BAV patients for whom valve replacement is not a suitable option.

An additional benefit of the study is that it provides insight into the development of BAV pathology through longitudinal imaging. It is likely that many of the patients who are enrolled as part of the “incompetent BAV” group and some who are enrolled as part of the “competent BAV” group will need to undergo surgical intervention within 5 years of the baseline scan. By imaging participants with 4D CTA on an annual basis, the study will provide information on the detailed morphological and dynamic changes that the BAV apparatus undergoes as patients develop worsening symptoms that necessitate surgical intervention. To the best of our knowledge, longitudinal 4D images have not before been acquired in this clinical context and can provide new insights into the timing of surgical intervention for future patients.

CONFIDENTIAL

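### Section 6.2.2 names Student t-tests; if they are applied at follow-up visits where the groups have become unequal, the error rate can drift either way, and Welch's test is a cheap safeguard

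*Protocol*

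**What the plan says.** **The test.** Protocol section 6.2.2 (Analysis of Primary Outcome of Interest) names "independent Student t-tests at multiple phases of the cardiac cycle" as the method for comparing the competent and incompetent groups. The same sentence adds a multiplicity correction based on the false discovery rate. The section does not use the words pooled or equal variance, and it states no alpha, sidedness or false discovery rate level.

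**Visits.** The t-test sentence names cardiac phases, not visits. The reference to study visits is in the preceding sentence on descriptive statistics: "including group means and standard deviations time-normalized with respect to the cardiac cycle at each study time point". The sentence after the t-tests leaves follow-up methods open: "We will perform additional statistics on longitudinal data".

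**Group sizes.** Section 3.1: "Each group will be limited to 30 patients". Section 6.1 enrols 30 per group so that at least 20 per group yield adequate images, without naming a visit.

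**Exit.** Under section 5.4 (Subject Withdrawal), patients who meet the indications for valve surgery stay on their timeline, "unless they require an aortic valve replacement, at which point they will end their study participation". Section 10.2 (Benefits) considers it likely that many incompetent and some competent patients "will need to undergo surgical intervention within 5 years of the baseline scan".

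**The concern.** The pooled t-test estimates one common variance and weights each group's variance by its degrees of freedom. If one group is smaller and the variances differ, the standard error is wrong, and its direction depends on which group is more variable. A smaller, more variable group makes the standard error too small and the test rejects too often. A smaller, less variable group makes it too large, and the test loses power.

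The protocol's exit rule and its own expectation about surgery point to a smaller incompetent group as follow-up proceeds. If 6.2.2 is applied visit by visit, the p-values passed to the false discovery rate procedure may then be miscalibrated. That procedure takes p-values as given and does not repair them. With 20 to 30 patients per group, drift in either direction matters: it produces either spurious anatomical differences or missed ones.

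**Working it through.** **Inputs from the protocol.** Student t-test (6.2.2); at most 30 per group (3.1); at least 20 evaluable per group (6.1). The protocol states no error rate, SD or power figure for this comparison, so there is none to reproduce. The sample-size arithmetic is consistent: 20 / (1 − 1/3) = 30, where the one-third loss is inferred from the 30 and the 20.

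**Assumptions.** Normal data, no true mean difference, two-sided 5% per test. The illustrative follow-up sizes are n1 = 30 competent and n2 = 20 incompetent, taking the protocol's cap for one group and its minimum for the other. The SD ratio r = SD(incompetent) / SD(competent) runs from 0.67 to 2, with the competent SD set to 1.

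**Step 1: formulas.**

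- True variance of the mean difference: V = 1/n1 + r²/n2.
- Average variance the pooled test uses: P = [((n1 − 1) + (n2 − 1)r²) / (n1 + n2 − 2)] × (1/n1 + 1/n2).
- Approximate actual error: the two-sided t tail area beyond t_crit / √(V/P).

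**Step 2: when nothing goes wrong.** If n1 = n2 = n, then V = (1 + r²)/n and P = [(1 + r²)/2] × (2/n) = V, whatever r is. If r = 1, V = P at any sizes. Simulation at 30:30 and 20:20 agrees: Student's error is about 5% for every ratio from 0.67 to 2. The planned baseline comparison is therefore safe.

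**Step 3: 30 versus 20.** Here t_crit on 48 degrees of freedom is 2.011. Worked for r = 1.5:

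- V = 1/30 + 2.25/20 = 0.1458
- P = [(29 + 19 × 2.25)/48] × 0.0833 = 0.1246
- V/P = 1.171, square root 1.082
- 2.011 / 1.082 = 1.858, tail area 6.9%

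| SD ratio r | V | P | √(V/P) | Student, formula | Student, simulated |
|---|---|---|---|---|---|
| 0.67 | 0.0558 | 0.0652 | 0.925 | 3.5% | 3.5–3.6% |
| 1 | 0.0833 | 0.0833 | 1.000 | 5.0% | 5.0% |
| 1.25 | 0.1115 | 0.1019 | 1.046 | 6.1% | 6.0–6.1% |
| 1.5 | 0.1458 | 0.1246 | 1.082 | 6.9% | 6.9–7.1% |
| 2 | 0.2333 | 0.1823 | 1.131 | 8.2% | 8.4–8.5% |

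The simulations used at least 100,000 null data sets per setting; ranges are over repeat runs. Welch's test gave 4.8 to 5.2% in these settings.

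**Step 4: sensitivity to size.** All of these sizes are assumed (competent:incompetent). Student's error at r = 0.67 / 1.25 / 1.5 / 2:

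- 28:20: 3.7 / 5.8 / 6.7 / 7.9%
- 27:15: 2.9 / 6.6 / 8.1 / 10.1%
- 25:10: 2.2 / 7.4 / 9.8 / 13.5%

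Welch stays at 4.9 to 5.2% in all of them.

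**Step 5: price of Welch if SDs are in fact equal.** Simulated power at the difference for which Student has 80%, Student against Welch:

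- 30:30: 79.7% against 79.7%
- 28:20: 79.9% against 79.6%
- 27:15: 80.2% against 79.3%
- 20:10: 80.0% against 78.1%
- 25:10: 80.0% against 77.2%

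**The case against.** A reader might infer that the plan fixes the pooled test for every visit, that the incompetent group is the more variable one, and that false positives will therefore rise to 10 to 14%. The documents do not support this.

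- **Variability.** No section gives an SD or says which group varies more. Section 1 gives both groups a band of severity (none to mild, moderate to severe). Replacement might also remove the most diseased valves and so narrow the incompetent group as it shrinks. The direction of the error depends on this unknown.
- **Visits.** The t-test sentence does not mention visits, and longitudinal methods are left open. A visit-by-visit comparison is a natural reading, because the measurements being compared are extracted and reported at each time point, but it is not stated.
- **Imbalance.** Section 10.2 speaks of surgery in general, whereas only replacement ends participation. Patients who have a repair stay in, and no split is given. Rates of 10% or more appear only at an SD ratio of 2 with 15 or fewer incompetent patients, sizes the protocol does not give.
- **False discoveries.** No false discovery rate level is stated. The figures above are unadjusted per-test rates, so they do not show how many false differences would be declared after adjustment.
- **Detail level.** The variant of a t-test is often settled in a statistical analysis plan, and section 6.1 frames the study as feasibility work.

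These points remove any claim of certain inflation and keep the matter minor. They do not remove the point itself: the protocol names a particular test for its primary comparison, that test is safe only with equal sizes or equal variances, and the protocol makes the first unlikely at later visits and gives no basis for the second.

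**Conclusion.** The point holds as a minor, conditional improvement. At the planned equal baseline sizes Student's test is sound. At follow-up, if the same tests are applied and the incompetent group has become smaller, per-test error before adjustment can fall below or rise above 5%. At 30 versus 20 the range is about 3.6% to a little over 8%, for SD ratios from 0.67 to 2. It is exactly on target only if the SDs are equal.

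The conclusion rests on the usual pooled reading of the test's name, on assumed follow-up sizes and SD ratios, and on normal data. The protocol supports the likely direction of the size imbalance but not its amount, and it supports no direction for the variance difference. The case for Welch does not need that direction, because Welch holds close to 5% either way.

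**What to change.** In section 6.2.2, name Welch (unequal-variance) t-tests in place of independent Student t-tests for the group comparisons, and report 95% confidence intervals for the mean differences on the same basis.

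This is a one-phrase edit with no effect on patients, visits or sample size. If the SDs turn out equal, the loss is under 0.5 points of power near the planned sizes and about 1 to 3 points at strongly unequal sizes (27:15 to 25:10).

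Welch addresses unequal variances only. If replacement selectively removes patients, later-visit means describe those who remain, and this change does not correct that.

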Approximately 95% of CT contrast reactions are mild to moderate in degree and most resolve without treatment. However, life-threatening reactions and fatalities, mostly of cardiovascular origin, have occurred. People with heart disease, kidney disease, or allergies are more likely to have a severe reaction to contrast agents. The patient will be instructed to inform the study staff if the patient has a history of heart disease, kidney disease, or allergies.

Common effects of iodinated IV contrast agents are:

- Feelings of overall warmth, especially in the bladder area after injection
- A metallic taste during the injection
- Warmth, burning sensation or momentary pain at the injection site during contrast injection
- Less common are nausea, vomiting, headache, hives and itching
- Rare, but serious reactions are rapid heartbeat, changes in blood pressure, heart attack, kidney failure, pulmonary edema, serious life-threatening allergic reaction.

Risk of IV Placement:

There is a possibility that multiple needle sticks will be necessary to ensure proper intravenous line placement. A small amount of pain or bruising may occur with intravenous catheter (IV) placement and there is a small risk of infection at the injection site.

Risks: CT Imaging and Incidental Findings

It is possible that during the course of the research study, the research staff (and/or radiologist that reviews the CT scan) may notice an unexpected finding(s). Should this occur, the finding (s) will be considered by the appropriate medical personnel and the study principal investigator will inform them, if necessary. These finding(s) may or may not be significant, and may lead to further testing (such as additional imaging studies, or biopsy). This may result in anxiety or harm to the patient due to the additional testing. The costs of such additional testing will not be covered as part of this research study.

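### Section 7 takes patients with severe adverse events out of the whole study, not just out of the research scan, so standard-of-care follow-up that the secondary objectives need is lost

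*Protocol*

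**What the plan says.** Section 7 (Safety and Adverse Events) has four statements that bear on this point, in this order:

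- Its scope: "Potential safety issues in this study are related to radiation and contrast for the 4D CT exam".
- The handling of the more serious reactions: "Moderate to severe contrast reactions will be reported to the IRB as severe adverse events and evaluated individually by the safety committee".
- The rule at issue: "Patients who have severe adverse events will be withdrawn from the study".
- The handling of the rest: "Mild reactions to contrast will be reviewed quarterly to evaluate whether the participant should continue in the trial".

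The protocol does not define a severe adverse event beyond the second of these.

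Section 5.4 (Subject Withdrawal) gives other ways out: the patient's own choice, being "discontinued from the study at the discretion of the Investigator for lack of adherence to study procedures or visit schedules", and aortic valve replacement. It does not list withdrawal for an adverse event. It adds "Patients will be followed for any safety events", without saying what is collected or for how long. Of patients who meet the indications for valve surgery it says "they will remain in the study on their original study timeline, unless they require an aortic valve replacement".

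The secondary objectives (Section 2.2) are the natural history of BAV disease and the anatomical predictors of successful repair. Section 3.2 takes AI and AS severity from routine echocardiography. Sections 3.1 and 5.2.2 describe the annual visits and echocardiograms as standard of care. Section 5.3 records operative information when valve surgery occurs.

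**The concern.** There are two faults. First, the safety committee is to consider moderate and severe reactions one at a time, but the next sentence settles the outcome. Staff cannot tell whether the committee's assessment has any bearing on participation.

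Second, the consequence reaches further than the hazard that prompts it. A contrast reaction is a reason to reconsider further contrast. It does not prevent anyone from reading the patient's next routine echocardiogram. As written, the rule ends both. A patient who reacts at the baseline scan contributes nothing to the natural-history objective afterwards, although the relevant tests would go on being done in ordinary care. With at most 30 patients per group, longitudinal data are scarce, and this loss is the protocol's own choice.

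**Working it through.** **Does the rule end data collection?** Each provision that might preserve follow-up was checked.

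- Section 5.4, safety follow-up: covers safety events only. It does not mention AI or AS severity, visits or echocardiography.
- Section 5.3, unscheduled visits and surgery: describes what is recorded for patients in the study. It does not extend to withdrawn patients.
- Section 8.1: asks for an attempt to obtain vital status when a patient revokes authorization for use of health information. There is no counterpart for safety withdrawals.
- Section 8.3: keeps the link to the medical record for completing data entry or for a later study. That is not planned follow-up.

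None of these continues the annual AI/AS assessment.

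**Is the sample size threatened?** Section 6.1 enrols 30 per group so that at least 20 have adequate images. No loss rate is stated, so it can only be solved backwards: 1 − 20/30 = 33.3%, and 20/(1 − 1/3) = 30.

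**How many patients might be affected?** The protocol gives no incidence of contrast reactions, so the following is an assumed range. Let q be the probability of a moderate or severe reaction at one scan, constant and independent across scans. Table 1 has five scans (years 0 to 4), and 60 patients are planned.

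- Withdrawn by the end: 60 × [1 − (1 − q)^5].
- Withdrawn before the last scan, and so losing at least one later annual assessment: 60 × [1 − (1 − q)^4].
- Post-baseline annual assessments lost, out of 60 × 4 = 240: 60 × [4q + 3q(1 − q) + 2q(1 − q)² + q(1 − q)³], because a reaction at scan k forfeits the 5 − k that remain.

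| q (assumed) | Cumulative risk, five scans | Withdrawn of 60 | Of these, before last scan | Assessments lost of 240 |
|---|---|---|---|---|
| 0.1% | 0.5% | 0.3 | 0.2 | 0.6 (0.25%) |
| 0.5% | 2.5% | 1.5 | 1.2 | 3.0 (1.2%) |
| 1% | 4.9% | 2.9 | 2.4 | 5.9 (2.5%) |
| 2% | 9.6% | 5.8 | 4.7 | 11.8 (4.9%) |

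Even at 2%, the 9.6% cumulative loss is well inside the 33.3% allowance. The table assumes that the rule covers contrast reactions only and that there is no other dropout.

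**The case against.** The strongest reply is that the effect is small and falls outside the main analysis. The one comparison that the protocol specifies (Section 6.2.2) uses 4D CTA measurements, which a patient who stops scanning could not supply under any rule. Section 6.1 already allows for withdrawals. A committee can also assess the severity and cause of a reaction even where withdrawal follows, so the two sentences are in tension rather than flatly opposed. What participants are told about data collection after withdrawal may stand in the consent form, which is not shown. All of this stands, and it limits the point to the secondary longitudinal data. It does not supply the missing follow-up provision.

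Three stronger readings are tempting, and the documents do not support them.

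- *Section 7 contradicts Section 5.4.* A reader might infer this because the withdrawal sentence has no stated limit, Table 1 schedules a general adverse event assessment at every study visit, and Section 10.2 expects many patients in the incompetent group to need surgery within 5 years. A severe event around a valve repair would then remove a patient whom Section 5.4 keeps. But Section 7 opens with radiation and contrast, and the sentences on either side of the rule concern contrast reactions. On that narrower and at least equally natural reading, Section 5.4 merely omits this exit. The conflict arises only if the term extends beyond scan-related events.
- *The rule makes progression or repair results look too good.* This needs withdrawn patients to fare worse than those who stay, and the protocol links contrast reactions to neither AI/AS progression nor repair durability. Even for events after surgery the sign is open. With invented counts of 10 repairs, 4 recurrences (40%) and 3 withdrawals, the proportion among the remaining 7 is 2/7 = 29%, 3/7 = 43% or 4/7 = 57% when 2, 1 or 0 of the withdrawn patients recur.
- *Section 10.1 contradicts classing moderate reactions as severe adverse events.* It says "Approximately 95% of CT contrast reactions are mild to moderate in degree and most resolve without treatment". That describes the frequency and course of mild and moderate reactions taken together. It does not say how a study should handle a moderate one.

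**Conclusion.** The point holds as a defect in how withdrawal is defined. The rule reads as automatic, includes moderate contrast reactions, rests on a term not otherwise defined, and sits awkwardly after a sentence promising individual assessment. It ends participation as a whole, and nothing visible in the protocol keeps the standard-of-care visit, echocardiography and surgical data coming.

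The consequence is avoidable loss of data for the natural-history and repair objectives. The true size cannot be derived from the protocol. The range of about 0.3 to 5.8 patients of 60 rests wholly on assumed per-scan rates and on the narrow reading of the rule; a broader reading would add an unknown number. The primary CTA comparison and the target of 20 evaluable patients per group are not put at risk by this rule alone. It is a cheap improvement worth making, not a threat to the study's main result.

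**What to change.** Amend Sections 7 and 5.4 together.

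1. Distinguish two states: no further research 4D CTA, and withdrawn from the study.
2. For a patient who stops 4D CTA for a safety reason and does not withdraw consent, continue to abstract standard-of-care visit, echocardiography and surgical data to the end of the planned follow-up.
3. State which events the withdrawal sentence covers, and add that exit to Section 5.4 so that the two sections agree.
4. Reconcile the withdrawal sentence with the one on individual evaluation, so that it is clear whether the committee's assessment can affect participation.

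How reactions are classified and who is scanned again are for the sponsor to settle; the change needs no position on either. The cost is a short amendment, a check that the consent form agrees with it, and a little more chart abstraction of data already generated in routine care.
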